2.3.2. Secondary Endpoints

- Assess symptoms of depression using the Montgomery-Asberg Depression Rating Scale (MADRS) prior to the primary endpoint at 1 week post psilocybin-assisted psychotherapy vs control psychotherapy.
- Assess symptoms of depression using the MADRS after psilocybin administration (for patients randomized to psilocybin or who receive open-label psilocybin) at 1 week, 4 weeks, 8 weeks, 12 weeks, and 6 months.
- Assess symptoms of burnout using the Stanford Fulfillment Index (SFI) at 4
 weeks post medication administration. We expect at least 50% of participants
 treated with psilocybin to show a reduction in the SFI work exhaustion and
 interpersonal disengagement subscales by at least 25% (from "a lot" to
 "moderately").
- Assess symptoms of burnout after psilocybin administration (for patients randomized to psilocybin or who receive open-label psilocybin) at 1 week, 4 weeks, 8 weeks, 12 weeks, and 6 months.
- Another secondary endpoint will assess symptoms of post-traumatic stress using the PCL5, measured at 1 week and 4 weeks after the medication session.
 We expect at least 50% of participants treated with psilocybin to show a reduction in PCL5 scores by at least 10 points (the clinically meaningful threshold for improvement).
- Assess symptoms of post-traumatic stress using the PCL5 after psilocybin administration (for patients randomized to psilocybin or who receive openlabel psilocybin) at 1 week, 4 weeks, 8 weeks, 12 weeks, and 6 months.
- A 10% or less difference in the rate of adverse events between the treatment and control arms at all study visits.

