9.2. Statistical approach

The primary objective of this randomized trial is to compare the mean change from baseline MADRS among patients randomized to receive psilocybin to that among patients randomized to receive niacin. The time point of primary interest at which change will be assessed will be 4 weeks. Mean change between the two groups will be assessed with the two-sample t-test, or the Wilcoxon rank-sum test if distributional assumptions for the t-test are violated. The table below shows the minimum detectable assumed-true effect size (represented in standard-deviation units, or the difference in mean change divided by the common standard deviation) to observe a statistically significant difference (at the two-sided significance level of .05) with 80% and 90% power for a variety of total sample sizes.

Sample size	80% Power	90% Power
N=30	1.06 SD units	1.23 SD units
N=40	0.91 SD units	1.05 SD units
N=50	0.81 SD units	0.94 SD units

Based on the values in the above table, we will randomize 30 patients, as we hypothesize that an assumed-true effect size of 1.06 – 1.23 is achievable based on previous studies by [name] and Davis and achieved effect sizes of 1.46 at 2 weeks at 1.69 at 6 weeks¹⁹ or 2.2 at 5 weeks.¹⁸ A sample size of N=30 will provide >90% power to detect a significant difference in the primary outcome between the psilocybin 25 mg vs niacin groups. Assuming a 15% drop-out rate of subjects in this study, we will enroll 36 subjects and assume 6 will not complete the study, so full enrollment in this study will be 36 with a target of 30 subjects completing the study.

The primary analysis will be done using the intent-to-treat principle. Randomization will be done using a permuted block design with randomly selected block sizes.

Key secondary endpoints include those listed below, and a hierarchical approach will be taken to the potential analysis of these endpoints. If the primary endpoint is statistically significant, then these secondary endpoints will be (potentially) formally compared in a hierarchical manner in the order listed below.

- 1. Mean change in burnout (Stanford Fulfillment index) from baseline to 4 weeks between the two groups
- 2. Mean change in symptoms of PTSD (PCL5) from baseline to 1 week and 4 weeks between the two groups.

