These secondary endpoints will be compared between groups as described above. At the first endpoint that is not statistically significant (at the two-sided significance level of .05), all subsequent endpoints will be evaluated descriptively and not formally assessed in order to maintain the overall type I error rate of .05.

10. Ethics/Protection of Human Subjects

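### The last step of the section 9.2 hierarchy holds two PCL5 comparisons with no rule for combining them, so the stated overall .05 is not guaranteed for that step

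*Combined protocol and SAP*

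**What the plan says.** Section 9.2 makes the 4-week MADRS change the primary comparison. If it is significant, the key secondary endpoints are to be "formally compared in a hierarchical manner in the order listed below". Two are listed. Item 1 is the change in the Stanford Fulfillment Index to 4 weeks, a single time point. Item 2, the last, is "Mean change in symptoms of PTSD (PCL5) from baseline to 1 week and 4 weeks between the two groups".

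On method, the section says "These secondary endpoints will be compared between groups as described above". That points back to the primary analysis: "Mean change between the two groups will be assessed with the two-sample t-test", with the Wilcoxon rank-sum test as fallback. At the first endpoint that is not significant at two-sided .05, "all subsequent endpoints will be evaluated descriptively and not formally assessed in order to maintain the overall type I error rate of .05".

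Section 2.3.2 describes the PCL5 endpoint in similar terms: "Another secondary endpoint will assess symptoms of post-traumatic stress using the PCL5, measured at 1 week and 4 weeks after the medication session". It expects at least half of psilocybin participants to "show a reduction in PCL5 scores by at least 10 points", but ties that target to neither time point.

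**The concern.** A fixed-sequence procedure needs one significant-or-not verdict per step. The method named for item 2 is a two-sample test of a mean change. No joint test or longitudinal model is described, so item 2 produces two p-values. The text does not say whether the two time points are taken in order, must both be significant, or may each support a claim alone. The stopping rule does not help, because it acts between listed endpoints and both PCL5 tests sit inside one.

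Two things are at stake. First, if either result may count, a PCL5 claim resting on one time point is not covered by the .05 that section 9.2 says it maintains. Second, the same data can lead to different formal conclusions depending on a rule that is not written down:

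- Only week 1 significant: ordered testing (week 1 first) and either-counts allow a week-1 claim; both-required allows none.
- Only week 4 significant: only either-counts allows a claim.

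**Working it through.** **Inputs from the documents.** Two-sided .05, stopping at the first non-significant endpoint, overall .05, and an assumed MADRS effect of 1.06 to 1.23 SD (all section 9.2); 15 per arm (section 6.1).

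**Assumed inputs, not in the documents.** The correlation between the two PCL5 tests, the burnout effect, the true PCL5 effect, and the correlations between endpoints. Ranges are shown for each.

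**1. The plan's own figures.** Noncentral-t power for a two-sample t-test at 15 per arm gives detectable effects of 1.060 SD (80% power) and 1.226 SD (90%), matching the tabulated 1.06 and 1.23. The overall .05 also holds through the primary and burnout steps, since each is one test at .05, reached only if the step before it is significant.

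**2. Error of the PCL5 step, given that it is reached and PCL5 is null at both times.** For two two-sided .05 tests with correlation ρ:

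- P(at least one) = 1 − P(|Z1| < 1.96 and |Z2| < 1.96); at ρ = 0 this is 1 − .95² = .0975.
- P(both) = .05 + .05 − P(at least one).
- Ordered testing: the first test alone decides whether any claim is possible, so the error is .05.

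| ρ | Either counts | Both required | Ordered |
|---|---|---|---|
| 0 | .0975 | .0025 | .05 |
| .5 | .0907 | .0093 | .05 |
| .7 | .0835 | .0165 | .05 |
| .9 | .0704 | .0296 | .05 |

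Simulated t-tests at 15 per arm (200,000 replicates) give .0972, .0916, .0842 and .0710 for either-counts.

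Independence is an extreme case, because both changes share one baseline. If baseline, week 1 and week 4 have equal variance σ² and equal pairwise correlation r, the covariance of the two changes is σ²(1 − r) and each variance is 2σ²(1 − r), so ρ = .5 whatever r is.

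**3. Counting the two earlier tests.** A false PCL5 claim also requires the primary and burnout tests to be significant. If those are independent of PCL5, the either-counts error exceeds .05 only when both pass with probability above .05/.0907 = .551 (ρ = .5) or .05/.0704 = .710 (ρ = .9). For example, with MADRS and burnout each at 1.23 SD, power is .9016 each; if independent, both pass with probability .9016² = .813, and .813 × .0907 = .074.

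Simulated either-counts error (15 per arm, 200,000 replicates per cell, PCL5 null, ρ of .5, .7 and .9, correlation with the earlier endpoints 0, .3 and .5):

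| Assumed burnout effect | MADRS 1.06 SD | MADRS 1.23 SD |
|---|---|---|
| 0 SD | .0026–.0092 | .0031–.0105 |
| .5 SD | .0151–.0318 | .0166–.0334 |
| .8 SD | .0325–.0465 | .0360–.0484 |
| 1.06 SD | .0425–.0583 | .0467–.0652 |
| 1.23 SD | .0457–.0662 | .0514–.0738 |

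Over the same cells the maximum is .0413 for ordered testing and .0238 for both-required.

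**4. How often the rules part.** With the same true PCL5 effect at both times, the probability that exactly one time point is significant, among trials reaching the step, is (ρ = .5, then .9): .272 and .122 at .5 SD; .335 and .146 at .8 SD; .230 and .104 at 1.06 SD. Both-required departs from either-counts in all of these, about 10 to 34%. Ordered testing departs from either-counts only when the later time point alone is significant. By symmetry that is half, from .104/2 = .052 to .335/2 = .168, or about 5 to 17%.

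**The case against.** The strongest reply is that the natural reading already controls the error. Endpoints are tested in listed order, item 2 names 1 week before 4 weeks, and the declared aim is an overall .05. Either-counts conflicts with that aim, and nothing in the documents states it. Moreover, .05 is attached to an endpoint, and section 2.3.2 treats the PCL5 pair as one endpoint, so .05 for each time point is an inference.

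Much of this stands. The ordered reading is available and the per-time-point .05 is inferred. But the listed order governs the numbered items, and treating the pair as a single endpoint fits either-counts or both-required as readily as ordered testing. Stating the aim of .05 does not supply the rule that achieves it.

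A reader might also infer that the plan's overall error is near .10. The documents do not support that. The .07 to .0975 is conditional on passing two earlier tests, on PCL5 being null at both times and on one of three possible readings. It is a legitimate worst case for a claim to maintain .05, but not the expected operating error.

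Finally, the consequence is limited: this is the last-ranked secondary step of a 30-person trial. That also stands.

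**Conclusion.** The point holds in a limited form. As written, section 9.2 does not secure its stated .05 for the PCL5 step, because it gives two p-values and no rule. If either may count, the error of that step, once reached, is about .07 to .09 at assumed correlations of .9 to .5, and .0975 under independence. Ordered testing or requiring both would keep .05, but neither is stated.

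Counting the earlier tests, with MADRS at the plan's 1.06 to 1.23 SD, no simulated cell exceeds .05 at a burnout effect of .8 SD or less (maximum .0484). Some do at 1.06 SD, and the highest value, at 1.23 SD, is .0738. The documents give no burnout effect, so where the trial falls in that range is unknown.

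A reader might infer that the primary or burnout conclusion is weakened. It is not: both come earlier in the sequence, at one time point each, and nothing in the PCL5 step can raise their error. The sample size is also untouched. The clarification should be made before any between-group analysis.

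**What to change.** Replace item 2 of section 9.2 with two single-test steps: PCL5 mean change from baseline at one time point (step 2), then at the other (step 3). Test each at two-sided .05 only if every earlier step is significant, and stop formal testing at the first that is not. The listed order is 1 week, then 4 weeks. The reverse also keeps .05. The choice is the sponsor's, provided it is fixed before any between-group analysis.

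This changes wording only, with no new visits or data. Ordered testing never allows fewer claims than both-required. With an assumed .8 SD at both times and the earlier tests passed, the first time point is claimed in .56 of trials and the second in .40 to .49, against .40 to .49 for any claim if both are required. The downside is that the second time point can be claimed only if the first is significant. With an assumed .5 SD at 1 week and .8 SD at 4 weeks, the 4-week claim is made in .21 to .26 of trials under the listed order, against .56 if 4 weeks is tested first.

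Optional and separate, not an error: section 2.3.2 also lists a MADRS comparison "prior to the primary endpoint at 1 week post psilocybin-assisted psychotherapy vs control psychotherapy", which section 9.2 does not place in the hierarchy. It could be added as the last step at no cost in alpha or power to the earlier steps. Its reach would be modest: claimed in .16 to .23 of trials if every endpoint has an effect of .8 SD, and .45 to .53 at 1.06 SD.

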10.1. Ethical Standards

The research will be performed according to ethical principles and in compliance with all federal, state, and local laws, as well as institutional regulations and policies regarding the protection of human subjects.

10.2. Informed Consent Process

After an initial phone screen to determine obvious exclusions from the study protocol, potential subjects will be invited for an in-office visit. During the screening visit, the study procedures will be described, and the subject's questions will be answered prior to obtaining an informed consent. The person obtaining the consent will ask the participant to provide a brief summary of the study to ensure they understand what is being asked of them and anypotential risks and benefits. For participants who are out of the area, informed consent will be obtained via video conference and written consent documented using REDCap.

10.3. Participant and Data Confidentiality

Participant study identification numbers (which cannot be linked to participant), names, and other demographic information, contact information, and previous medical history will be kept in a locked filing cabinet located in a locked room. Secure research files will be used to store assessment and data forms derived from the research data collection. Each participant is assigned a numeric code to conceal identity. This coding will carefully safeguard confidentiality on encrypted computer hard disks used for analysis. No personal identifying data will appear in the computerfiles or other papers (e.g., questionnaires, laboratory raw data).

Page 37 Version 1.16, July 18, 2022

Care will be taken to conceal other possible sources of identification, including addresses or occupations. A list of participant numbers, names, and other demographic information will be kept in a locked cabinet located in a locked room. Cross-referenced names and code numbers will be included in a master list that will be stored in a locked file cabinet that will be accessible only to the research staff. Theidentities of participants will not be revealed in any description or publications resulting from this research. The granting agency, the research monitors, the Pl's laboratory, and collaborators will have access to de-identified study data. All electronic data is double password-protected and follows IRB standards at the University of Washington. Digital data will be stored on a secured server and on secured desktop computers.

10.4. Research Use of Stored Human Data

The investigators understand the importance of communicating research findings from studies. Results from this study may be presented at conferences and meetings or published

in academic journals. All data would be deidentified and participant identity would never be disclosed when presenting results of the study.

10.5. Future Use of Stored Data

De-identified data may be stored indefinitely and used for publications, research presentations and meetings.

11. Data Handling and Record Keeping

11.1. Data Collection and Management Responsibilities

The principal investigator, [name], will be responsible for monitoring the data, assuring protocol compliance, and conducting the safety reviews at the specified frequency, which must be conducted at a minimum of every 6 months. [name] will confer and discuss any issues with the research and oversight team that have been brought to light and will discuss what alterations might be needed if any, in weekly rounds meetings (as is the clinic standard research practice). Any adverse events will be reported in accordance with University of Washington policies.

During the review process, the principal investigator and the Medical Monitor will evaluate whether the study should continue unchanged, require modification/amendment, or close to enrollment. Either the principal investigator, the IRB, or University of Washington administrators have the authority to stop or suspend the study or require modifications.

Research personnel will collect research data via direct interview after potential subjects' sign release of information for available informants. This data will be recorded in both written and/or electronic formats, and all confidential research data will be separated and stored in locked and secured files.

11.2. Study Records Retention

All electronic research records will continue to be encrypted and password-protected after subject participation. Both written and electronic records will be destroyed 10 years after the protocol is completed.

12. Publication and Data Sharing Policy

The identities of participants will not be revealed in any description or publications resulting from this research. The granting agency, the research monitors, the PI's laboratory, and collaborators will have access to de-identified study data.

13. Study Administration and Leadership

